5.2 Institutional Review Board (IRB) Review

The protocol will be submitted to the IRB for review and approval. Approval of the protocol must be obtained before initiating any research activity. Any change to the protocol or study team will require an approved IRB amendment before implementation. The IRB will determine whether informed consent and HIPAA authorization are required.

A study closure report will be submitted to the IRB after all research activities have been completed.

5.3 Subject Confidentiality

Participant confidentiality and privacy is strictly held in trust by the participating investigators, their staff, and the sponsor(s) and their interventions. Therefore, the study protocol, documentation, data, and all other information generated will be held in strict confidence. No information concerning the study or the data will be released to any unauthorized third party without prior written approval of the sponsor.

All research activities will be conducted in as private a setting as possible.

The study monitor, representatives of the Institutional Review Board (IRB), or regulatory agencies may inspect all documents and records required to be maintained by the investigator, including but not limited to, medical records (office, clinic, or hospital) for the participants in this study. The clinical study site will permit access to such records.

At the end of the study, all records will continue to be kept in a secure location for 7 years. Study participant research data, which is for purposes of statistical analysis and scientific reporting, will be transmitted to and stored on Yale redcap servers and in locked cabinets in locked office at CMHC. This will not include the participant's contact or identifying information. Rather, individual participants and their research data will be identified by a unique study identification number. The study data entry and study management systems used will be secured and password protected. At the end of the study, all study databases will be de-identified and archived on Yale servers and CMHC.

Identifiable information including participant's name, address, phone number, and date of birth, will be collected and used to enroll and contact participants. It will only be used for this purpose. This information will be stored in locked cabinet apart from the research records.

Research data will be collected using interviews, self-reports, wearable devices, and computer tasks. All identifiable information will be stored in a locked research cabinet. All participants will be assigned a study participant number. Subsequently, participants will be identified in the Case Report Forms (CRFs) only by that number and an encoded version of their initials (i.e., John Doe = JDO). A list of numbers and the corresponding names will be maintained by [name] and stored in a locked research cabinet.

The data will be stored on secured server, laptop computer and desktop computer. The data will be stored in a locked room for 7 years after the final data is collected. After this point, the Data Manager and Principal Investigator, [name], will oversee the process in which data is destroyed or de-identified.

Several steps will be taken to safeguard the confidentiality of subjects and their data. All research data that is collected will be assigned a study participant number and that number will only identify participants in digital databases. The names of participants will not be associated with this data and assessments will be maintained according to participant study number. A master list connecting participant study numbers to participant names will be kept in a locked file cabinet where it can only be accessed by senior level project staff. Any information published as a result of the study will be such that it will not permit identification of any participant.

Right to privacy for participation in this research will be protected through alphanumeric coding of data (in place of names) and proper storage of research records, including treatment exit interviews. Collected materials will be maintained via an alphanumeric reference system maintained by [name]. Participants' names will appear only on the compound authorization form, and a master list maintained in a physically locked file that is separate from research data. Our data collection and management procedures are fully compliant with HIPAA. Access will be limited to personnel intimately involved in the study. A Certificate of Confidentiality will also be obtained from the National Institutes of Health to protect access to the records. However, participants will also be told that if they present with suicidal or homicidal ideation and/or report any form of child/elder abuse or report plans to damage property then we will have to report this to the appropriate authorities and/or provide them with referrals for immediate treatment. Electronic data will be de-identified, and password protected. Only members of the study team will have access to the physical or electronic data.

For the wearable devices, data will only be linked to participants' study numbers not the participants themselves. Only members of the study team will have access to the physical or electronic data. OURAM™ data are deidentified and are also protected through secure, password-protected servers. We will use an alphanumeric code to sign participants up to the OURAM™ mobile app in place of their names. After downloading the data, the data will be immediately deleted from the devices. OURAM follows strict policy guidelines relating to both health privacy and teams privacy. OURAM™ complies with all legal requirements regarding data sharing and only shares user information with trusted service providers. Users can withdraw consent from having their data collected at any time. OURAM™ teams is a feature that allows health data to be shared with trusted individuals, such as healthcare professionals and researchers. There are safeguards in place to ensure this data is processed and collected efficiently and appropriately, users can withdraw from providing data to OURAM™ teams at any time.

All investigators and key personnel have taken the required Yale University HIPAA training. Right to privacy for participation in this research will be protected through coding of data and proper storage of research records. A list of numbers and the corresponding names will be maintained by the Principal Investigator in a locked research cabinet.

Individually identifiable health information will be protected in accordance with the Health Insurance Portability and Accountability Act of 1996 and by additional protections of substance abuse treatment records afforded under Code of Federal Regulations (CFR) Part 2, Subpart E. All research personnel will be trained on human subjects' protection and HIPAA procedures.

We may share participant information with:

- The U.S. Department of Health and Human Services (DHHS) agencies
- Representatives from Yale University, the Yale Human Research Protection Program and the Institutional Review Board (the committee that reviews, approves, and monitors research on human participants), who are responsible for ensuring research compliance. These individuals are required to keep all information confidential.
- Those representatives at Yale who are responsible for the financial oversight of research including billings and payments
- The Principal Investigator
- The study sponsor
- Laboratories and other individuals and organizations that analyze your health information in connection with this study, according to the study plan
- Co-Investigators and other investigators
- Study Coordinator and Members of the Research Team

- Other researchers through a shared data agreement through a required policy from NIAAA

5.4 Deviations/Unanticipated Problems

A protocol deviation is any noncompliance with the study protocol. The noncompliance may be either on the part of the participant, the investigator, or the study site staff. As a result of deviations, corrective actions are to be developed by the site and implemented promptly. It is the responsibility of the site investigator to identify and report deviations within 2 working days of identification of the protocol deviation. All deviations must be addressed in study source documents, reported to the study sponsor, and the reviewing Institutional Review Board (IRB) per their policies.

Unanticipated problems involving risks to participants or others include, in general, any incident, experience, or outcome that meets all of the following criteria:

Unexpected in terms of nature, severity, or frequency given (a) the research procedures that are described in the protocol-related documents, such as the Institutional Review Board (IRB)-approved research protocol and informed consent document; and (b) the characteristics of the participant population being studied;

Related or possibly related to participation in the research (“possibly related” means there is a reasonable possibility that the incident, experience, or outcome may have been caused by the procedures involved in the research); and

Suggests that the research places participants or others at a greater risk of harm (including physical, psychological, economic, or social harm) than was previously known or recognized.

The investigator will report unanticipated problems (UPs) to the reviewing Institutional Review Board (IRB) and to the study sponsor. The UP report will include the following information:

Protocol identifying information: protocol title and number, PI's name, and the IRB project number;

A detailed description of the event, incident, experience, or outcome;

An explanation of the basis for determining that the event, incident, experience, or outcome represents an UP;

A description of any changes to the protocol or other corrective actions that have been taken or are proposed in response to the UP.

To satisfy the requirement for prompt reporting, UPs will be reported using the following timeline:

UPs that are serious adverse events (SAEs) will be reported to the IRB and study sponsor, if applicable immediately (if possible) followed by a written report within **5 calendar days** using the appropriate forms from NIH and Yale University IRB.

Any other UP will be reported to the IRB and study sponsor within 14 calendar days of the investigator becoming aware of the problem.

All UPs should be reported to appropriate institutional officials (as required by an institution's written reporting procedures), the supporting agency head (or designee), and the Office for Human Research Protections (OHRP) within 30 calendar days of the IRB's receipt of the report of the problem from the investigator.

5.5 Data Quality Assurance

Describe the quality control and assurance for the conduct of the study to ensure that Good Clinical Practice is followed. Any steps that will be implemented as part of the study to ensure standardization of the collection of accurate, consistent, complete and reliable data, such as training sessions, monitoring of investigator sites, instruction manuals, use of central laboratory or reading center should be included.

Multiple measures are in place to ensure the validity and integrity of the data. First, all research staff receive Human Subjects Protection training, as well as training in Good Clinical Practice. Second, [name] will supervise and train the Research Coordinator and key personnel on study procedures to ensure that all procedures are followed and are in compliance with the approved Yale University IRB protocol. [name] will also provide training and oversight to study staff to ensure data are generated, documented, and reported according to requirements by the Yale University IRB and NIH. She will then monitor adherence to protocol procedures and use individual supervision to address any data quality concerns. Third, weekly research meetings will be held for all research staff as a forum for in-service training as well as to discuss questions regarding issues that arise in complex clinical research protocols. Fourth, all research staff will be cross-trained to 'cover' for each other; thus, review by multiple staff with oversight by the PI will facilitate early identification of errors and oversight. Fifth, [name] will also oversee quality assurance of data. The Research Coordinator, in collaboration with [name], will review the study database on a monthly basis to ensure data accuracy. Any data quality issues will be addressed immediately. Last, the use of an electronic system for data capture will minimize data entry errors.

5.6 Study Records

Specify the documents considered study records (subject diaries, regulatory documents, protocols, consents forms, case report forms, subject medical records, surveys, specimens, etc.).

- Protocol
- Consent form
- Alcohol/sleep diaries
- Surveys

5.7 Access to Source

Source data will be maintained per Medical Records policy in a password protected, secure, Health Insurance Portability and Accountability Act (HIPAA) compliant, web-based electronic database with a built-in audit trail.

Only Institutional Review Board (IRB) approved research team members who have current HIPAA and Collaborative Institutional Training Initiative (CITI) Good Clinical Practice (GCP) and human subjects protection training will be authorized to access records.

5.8 Data or Specimen Storage/Security

Describe method in which data will be collected, stored (digital, hard copy, etc.) and maintained in a secure manner (encryption, password protection, etc.).

Data Acquisition and Transmission. We have selected psychometrically sound assessments that are brief and feasible with young adults and adequate to test study hypotheses. Trained research staff will administer assessments and collect measurements. They will enter data directly into a secure electronic database, which will be backed up on a secure, password protected Yale University network drive. De-identified data will be stored in the database and only accessible by research staff using a password protected login. All data with identifiable information will be stored in locked file cabinets in locked offices and will only be accessible by research staff. The transfer of any identifiable administrative data will be through Yale University's secure, password-protected Secure File Transfer system. OURATM data will also be de-identified and distributed to Yale through an agreement with OURATM that ensures data confidentiality.

Data Entry Method. Trained research staff will enter data directly into the electronic database. No personally-identifiable information will be entered into the electronic database, which will be stored on a secure, password protected Yale University network drive.

5.9 Retention of Records

The data will be stored in a locked room for 7 years after the final data is collected. After this point, the Data Manager and Principal Investigator, [name], will oversee the process in which data is destroyed or de-identified.

5.10 Study Modification

Study modifications will be undertaken in response to ongoing study monitoring. Any potential modifications that could have a major impact on the study objectives will be discussed with the NIH Program Officer before submission to the IRB. More minor modifications that do not impact study objectives but help with study recruitment and implementation or allow for additional assessment of important questions will be submitted to the IRB for approval.

5.11 Study Monitoring

[name], the PI, will be responsible for monitoring the data, assuring protocol compliance, and conducting the safety reviews at the specified frequency that must be conducted at a minimum of every 6 months (including when reapproval of the protocol is sought), which is appropriate for a study deemed to be of minimal risk. [name] will review the frequency of anticipated and unanticipated adverse events overall and by study arm with key personnel. The focus of the evaluation will be to determine whether the study should continue unchanged, require modification/amendment, continue or close to enrollment. [name], the Yale University IRB, and the National Institutes of Health have the authority to stop or suspend the study or require modifications.

[name] will also lead a weekly research meeting with key personnel to review the status of all enrolled participants and discuss the eligibility of potential participants. At this weekly meeting, [name] will review study progress (i.e., recruitment goals, retention, protocol adherence). Any adverse events will be reviewed at this meeting including serious adverse events that may have been attended to outside of this weekly meeting. An annual progress report will be submitted to NIH and the Yale University IRB that lists and summarizes adverse events; documents whether adverse event rates are consistent with pre-study assumptions; summarizes recruitment and retention and reason for dropouts; and summarizes study progress related to the stated aims.

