1.5 Potential Risks and Benefits

1.5.1 Potential Risks

The major potential risks in this study are related to intervention components, interviews/self-report questionnaires, urine collection, and recording of treatment exit interviews.

Intervention Components:

PPG sensor use and mobile self-monitoring of alcohol use and health behaviors poses minimal risk. There are no side effects from wearing the OURATM beyond minor inconvenience – users can shower and swim with the devices. OURATM deidentifies user data and will distribute data to us using deidentified data via a password-protected dashboard that protects participants' confidentiality. The brief health advice provided by the OURATM mobile app and our personalized alcohol-related feedback and advice pose minimal risk. A great deal of this information is also available to young adults through external health websites. Our experience providing brief alcohol and health interventions to young adults and cognitive-behavioral sleep interventions indicates that they are well tolerated. Our research group has several PhD-level clinical psychologists available for consultation should the need arise. Participants will be monitored regularly through daily diaries and via remote reminders regarding study procedures.

The Oura ring is a wearable ring that includes multiple sensors to detect several health biomarkers including temperature, sleep, heart rate and connects to mobile application that provides users with information about their health status. Participants will wear the device and half will have access to the mobile application to view their health data so we can test the effect of using this device and receiving this health information on drinking behavior. The device is not FDA approved and it is our understanding that they are not seeking FDA approval status at this time for any medical indications. The Oura ring is intended for general health self-monitoring and is available to the public.

These will only be given to participants and tested by research staff. They will be stored in a locked cabinet in a locked research office at CMHC in between use. The devices will also be cleaned in between use by different participants.

Interviews and Self-Reports:

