4.1.2 Adverse Events Definition and Reporting

[name], the principal investigator is responsible for monitoring the data, assuring protocol compliance, and conducting monthly safety reviews. During the review process, [name], will evaluate whether the study should continue unchanged, require modification/amendment, or close to enrollment.

[name], the Institutional Review Board (IRB) or NIH have the authority to stop or suspend the study or require modifications.

This protocol presents minimal risks to the subjects and Unanticipated Problems Involving Risks to Subjects or Others (UPIRSOs), including adverse events, are not anticipated. In the unlikely event that such events occur, Reportable Events (which are events that are serious or life-threatening and unanticipated (or anticipated but occurring with a greater frequency than expected) and possibly, probably, or definitely related) or Unanticipated Problems

Involving Risks to Subjects or Others that may require a temporary or permanent interruption of study activities will be reported immediately (if possible), followed by a written report within 48 hours of [name] becoming aware of the event to NIAAA and within 5 days per the guidelines of the Yale IRB (using the appropriate forms from the website) and any appropriate funding and regulatory agencies.

[name] will apprise fellow investigators and study personnel of all UPIRSOs and adverse events that occur during the conduct of this research project. [name] will hold weekly study meetings with investigators to review study progress, including any adverse events. Investigators who are not present at these meetings will be alerted via email by [name]. The protocol's research monitor(s), e.g., the Yale IRB and NIH will be informed of any adverse events that meet these 3 criteria: (1) unexpected, (2) related/possibly related to study participation, and (3) places subjects or others at greater risk of harm than previously known/recognized. These adverse events will be reported within 48 hours of the event becoming known to [name].

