Treatment Phase (Intake-Week 6): They will begin wearing the OURAM™ after the intake every day for a 6-week period. During these weeks, monitoring will occur continuously with the OURAM™ and subjects will also complete daily diaries using the MEI Research application. We will arrange to pick up the biosensor from them at the end of the 6-week monitoring period. If they are in the Feedback group, subjects will also receive health feedback and advice through the OURAM™ mobile app and reports that are sent to . The OURAM™ app provides daily summaries of their resting heart rate, heart rate variability, and sleep that they can view on the app. The research staff will orient them to the OURAM™ app health feedback and advice. In addition, every 2 weeks (i.e., Weeks 2, 4, and 6), we will send a written report via text/email that: (1) summarizes their alcohol use and the links with their heart and sleep health data and (2) provides health advice tailored to this data.

Follow-up (Week 6): Subjects will complete the Week 6 follow-up visit remotely via ZOOM, which will be recorded using ZOOM with their consent. The research staff will conduct exit interviews and treatment evaluation surveys to understand the feasibility/acceptability of the health intervention program including wearing the biosensor. They will also complete questionnaires and interviews about their alcohol use, health characteristics, and the feasibility and acceptability of self-monitoring activities and health feedback/advice.

Follow-Up (Week 10): Subjects will also complete the Week 10 follow-up visit remotely via ZOOM, which will be recorded using ZOOM with their consent. They will complete questionnaires and interviews about your alcohol use and health characteristics.

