4.3.3 Study Visits (is applicable)

Table 1. Schedule of Assessments

Variables	Assessments	Intake	Intake-Wk 6	6, 10
Eligibility/ Lab/ Medical	Demographics	X		
		X		
	The M.I.N.I.	X		
	AUDIT-C	X		
Alcohol/ Health Outcomes	TLFB	X		6, 10
	PROMIS™ measures	X		6, 10
	Physical fitness	X		6, 10
	BYACCQ	X		6, 10
	PSQ	X		6,10
	TPB	X		6
		X		6, 10
	DSQ	X		6,10
	Munich Chrono Type Questionnaire	X		
	ME Questionnaire	X		
	Alcohol/sleep diaries		X	
	COVID-19 Experiences Questionnaire	X		6,10
	OURA™ HRV, RHR, sleep		X	
Feasibility	OURA™ use metrics		X	
Acceptability	Treatment eval; exit interview			6

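### Section 5.11 promises adverse event frequencies by arm and a check against pre-study assumptions, but no described procedure asks participants about adverse events and no expected rate is stated

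*Combined protocol and SAP*

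**What the plan says.** Section 5.11 makes two commitments. The principal investigator "will review the frequency of anticipated and unanticipated adverse events overall and by study arm with key personnel", to help decide whether the study continues unchanged, is modified or closes to enrollment. The annual progress report to NIH and the IRB is one that "documents whether adverse event rates are consistent with pre-study assumptions".

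The pre-study position appears in two places. Section 4.1.2 says that unanticipated problems, "including adverse events, are not anticipated". Section 1.5.1 says of the ring: "There are no side effects from wearing the OURATM beyond minor inconvenience". Neither gives a rate.

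On collection:

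- **Table 1 (sections 4.1.1 and 4.3.3).** No named row covers adverse events. The nearest post-baseline row is "Treatment eval; exit interview", at Week 6, which serves acceptability.
- **Visits (section 4.2).** Week 6 covers alcohol use, health characteristics, feasibility and acceptability. For Week 10 the text reads: "They will complete questionnaires and interviews about your alcohol use and health characteristics".
- **Diaries (Synopsis and section 4.1).** They record alcohol use and sleep.
- **Weekly staff contact (section 1.5.1).** Its stated purpose is reminders and solving logistical problems.

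Sections 4.1.2 and 5.11 say how events are reviewed and reported once known. They do not say how staff learn of them.

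**The concern.** A frequency by arm needs a defined way of finding events that is the same for everyone. Without a prompt, the count depends on which participants happen to mention something and on which staff member recognises it as an adverse event. Events never asked about cannot be recovered at analysis, so this is more than a missing detail of wording.

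The check against pre-study assumptions has a separate weakness. It needs a stated expectation, and the documents offer only the general remark that events are not anticipated. The annual report would have no rate to compare with.

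What is at stake is how a low or zero count can be read. If it comes from unsolicited reports, it says less about the true rate than the sample size alone would allow.

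**Working it through.** **Step 1: is there a figure to reproduce?** No. The documents state no adverse event rate, observed or assumed.

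**Step 2: compare the commitments with the means of meeting them.**

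| Commitment in 5.11 | What it needs | What the documents give |
|---|---|---|
| Event frequency overall and by arm | A defined, identical query in both arms | No query in any named Table 1 row or in the visit, diary or weekly-contact text |
| Rates compared with pre-study assumptions | A stated expected rate or equivalent | A qualitative statement in 4.1.2 only |

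Both copies of Table 1 show an unlabelled row at intake. The copy in 4.3.3 also shows an unlabelled row at intake and Weeks 6 and 10. These labels may have been lost when the PDF was read, so the table alone does not prove absence. The visit text in 4.2 is independent of the table and describes no such question.

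**Step 3: what a zero count can say with full capture.** Input: n = 30 per arm (section 3.3.1). The one-sided 95% upper bound after 0 events in n is

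1 − 0.05^(1/n)

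- n = 30: 1 − 0.05^(1/30) = 9.5%
- n = 60, both arms pooled: 1 − 0.05^(1/60) = 4.9%

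**Step 4: what it can say with partial capture.** Suppose a share c of participants with an event is recorded. The recorded rate is then c times the true rate, and the bound on the true rate is 9.5% / c. The documents give no value for c, so these are assumptions:

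| Capture c | Upper bound on true rate after 0 of 30 |
|---|---|
| 100% | 9.5% |
| 75% | 9.5% / 0.75 = 12.7% |
| 50% | 9.5% / 0.50 = 19.0% |
| 25% | 9.5% / 0.25 = 38.0% |

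**Step 5: the same point as a probability.** Take an assumed true rate of 10%. The chance that an arm of 30 shows no event is (1 − 0.10c)^30:

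- c = 100%: 0.90^30 = 4%
- c = 50%: 0.95^30 = 21%
- c = 25%: 0.975^30 = 47%

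A clean record is unlikely at that rate with full capture, and close to an even chance if only a quarter of events are captured.

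**The case against.** The strongest reply is that this is a minimal-risk pilot. Adverse events are not an aim, an outcome or a planned analysis. Participants have at least weekly staff contact and daily diaries, which section 1.5.1 presents as safeguards, and staff review any events every week. The statement that events are not anticipated can be read as an assumption of a rate near zero. Even perfect capture leaves a 9.5% bound, which a new question cannot lower.

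Much of this stands. It limits the consequence to safety monitoring and reporting, and small numbers remain a major constraint. It does not answer the core point: section 5.11 promises frequencies by arm, and contacts at which a participant might mention an event are not a query. If a near-zero rate is the intended assumption, 5.11 should say so.

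A reader might infer more than the documents support:

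- **That reports would be lost.** The trigger for events "anticipated but occurring with a greater frequency than expected" has no stated frequency behind it. But if nothing is anticipated, a serious and related event qualifies as unanticipated under the same definition in 4.1.2.
- **That 4.1.2 and 5.4 classify the same event differently.** Section 5.4 judges expectedness partly by "the characteristics of the participant population being studied". For informing the research monitors, however, 4.1.2 uses the same three criteria as 5.4. Its remark about what is anticipated is a forecast and sets no classification rule.
- **That the Feedback arm has more staff support and so more chances to report.** Ring support (4.1) and weekly contact (1.5.1) are given to all participants. App orientation takes place at intake, and the reports arrive as text or email links.
- **That the alcohol-consequences questionnaire leaves a measurable gap in safety recall.** It is an outcome measure and is not described as adverse event collection. Its recall period appears only in the title of a cited article.

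**Conclusion.** The concern holds as a gap in safety collection. Section 5.11 promises by-arm frequencies and a rate comparison, while the described procedures contain no adverse event query and no expected rate.

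In size, a zero count in an arm of 30 supports an upper bound of 9.5% only under full capture, about 19% if half of events are captured, and 13% to 38% across capture of 75% down to 25%. The 9.5% follows from the planned arm size. The capture shares are assumptions.

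Two limits apply. Reliance on unsolicited reports is inferred from the absence of any described query, and some Table 1 row labels are missing in the text available. Nothing here shows that the intervention is unsafe, that required reports would be missed, or that under-recording would favour one arm. The efficacy analyses are unaffected.

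**What to change.** 1. Add one row to both copies of Table 1: a single scripted adverse event question, worded identically in both arms, at the existing Week 6 and Week 10 visits, with recall since the last visit. Week 6 then covers the period from intake and Week 10 the period from Week 6. Mention the question in the visit text of 4.2.
2. In 5.11, base the by-arm review on the answers to this question.
3. In 5.11, either state the pre-study assumption to be compared (for example, that no related serious events are expected) or drop the comparison.

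I would not add a list of expected alcohol-related events while also removing the rate comparison. That would move such events out of the unanticipated category into one that needs an expected frequency, with none stated.

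The cost is a minute or two at each of two visits, plus wording in Table 1, 4.2 and 5.11. Recorded event counts will be higher, and reports should explain that this reflects active questioning.
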